### **5.0 CRITERIA FOR SUBJECT ELIGIBILITY**

#### **5.1 Subject Inclusion Criteria**

##### **Aim 1: Part 1**

Patients must:

- Have completed treatment for head and neck cancer at least 1 year prior to survivorship visit and have no evidence of disease
- Be able to provide informed consent
- Be able to speak and read English
- Be at least 18 years old

##### **Aim 1: Part 2**

Patients must:

- Have completed treatment for head and neck cancer at least 1 year prior to survivorship visit and have no evidence of disease
- Have a primary care provider
- Be able to provide informed consent
- Be able to speak and read English
- Be at least 18 years old

## 5.2 Subject Exclusion Criteria

Subject exclusion criteria for patients recruited to Aim 1: Parts 1 and 2 is the same.

- Patients or providers who cannot speak or read English
- Patients with cognitive, visual, or motor impairment such that they cannot complete the Survivor Self-Assessment as assessed by the research team.

## 6.0 RECRUITMENT PLAN

### Recruitment Plan (with Limited waiver of Authorization)

Potential research subjects will be identified by a member of the patient's treatment team, the protocol investigator, or research team at Memorial Sloan Kettering Cancer Center (MSKCC).

The principal investigator may also screen the medical records of patients with whom they do not have a treatment relationship for the limited purpose of identifying patients who would be eligible to enroll in the study and to record appropriate contact information in order to approach these patients regarding the possibility of enrolling in the study.

During the initial conversation between the investigator/research staff and the patient, the patient may be asked to provide certain health information that is necessary to the recruitment and enrollment process. The investigator/research staff may also review portions of their medical records at MSKCC in order to further assess eligibility. They will use the information provided by the patient and/or medical record to confirm that the patient is eligible and to contact the patient regarding study enrollment. If the patient turns out to be ineligible for the research study, the research staff will destroy all information collected on the patient during the initial conversation and medical records review, except for any information that must be maintained for screening log purposes.

In most cases, the initial contact with the prospective subject will be conducted either by the treatment team, investigator or the research staff working in consultation with the treatment team. The recruitment process outlined presents no more than minimal risk to the privacy of the patients who are screened and minimal PHI will be maintained as part of a screening log. For these reasons, we seek a (partial) limited waiver of authorization for the purposes of (1) reviewing medical records to identify potential research subjects and obtain information relevant to the enrollment process; (2) conversing with patients regarding possible enrollment; (3) handling of PHI contained within those records and provided by the potential subjects; and (4) maintaining information in a screening log of patients approached (if applicable).

This limited waiver applies only to MSK. HH will obtain a limited waiver of authorization for their site.

### Aim 1: Part 1: Component pilot testing

*Head and neck cancer survivors.* Aim 1: Part 1 will be completed at MSK. We will recruit 10 patients (meeting eligibility criteria described in Section 5.0, above) to participate in end-user testing with a Research Study Assistant (RSA) before and after an HN-STAR-guided routine clinic visit. Patients scheduled to be seen at the Head and Neck Cancer Survivorship Clinic at MSK will be screened for eligibility Two weeks before each patient's scheduled survivorship clinic visit, eligible head and neck cancer survivors will be invited by mail to participate in the HN-STAR study. A consenting professional will follow-up with a phone call. At least three attempts will be made to reach the patient by phone. When the consenting professional reaches the patient by phone, she will describe the study and invite interested and eligible patients to participate. During the phone call, the consenting professional will follow a standard consent script that describes the study and confirms eligibility. Interested and eligible participants will be asked to provide consent. Participants who are not interested in participating will not be contacted again. As part of the verbal consenting process, reasons for non-participation may be asked in order to identify whether the study recruitment strategy is adequate. Patients will be consented over the phone before arriving to the clinic for their visit.

Because we want to sample a range of responses representing a diverse group of survivors, we will enrich for minorities in this group by enrolling no more than 7 white non-Hispanic patients. After enrolling 7 white non-Hispanic patients, if we have not yet enrolled 10 total patients, we will only invite non-white or Hispanic patients to participate until 10 patients enroll. With over 20 new survivors seen in the Head and Neck Cancer Survivorship Clinic at MSK clinic each month, this will not hinder enrollment.

Patients who participate in Aim 1: Part 1 of the study, will receive \$100 to provide thanks for their time and effort and a voucher to cover their parking fee, for those participants who drive.

*NP.* We will be asking the MSK NP to provide feedback (via survey and interview) about her experience using HN-STAR. Through the consent process, participants will understand that their NP will be surveyed and interviewed about HN-STAR as part of the study. The NP responsible for head and neck cancer survivors will be asked to provide written consent to participate.

### Aim 1: Part 2: Feasibility in clinical practice

There is a designated RSA at MSK and HH who will be responsible for recruitment, enrollment, data collection and study management at their respective site.

*Head and neck cancer survivors.* We will recruit an additional 45 survivors (30 from MSK and 15 from HH) to participate in Aim 1: Part 2 for feasibility testing. Patients who are eligible, scheduled, or due to be seen at the survivorship clinic at MSK and HH will be invited by mail to participate in the HN-STAR study. The patient will be able to opt out of the study by contacting the RSA. If the patient does not opt out, research staff at MSK or HH will follow-up with a phone call. At least three attempts will be made to reach the patient by phone. When the consenting professional at the respective site reaches the patient by phone, she will describe the study and invite interested and eligible patients to participate. The consenting professional will follow a standard consent script as described above. Patients will be consented over the phone with the RSA from their respective study site before completing the

Survivor Self-Assessment before the clinic visit. However, unlike Aim 1: Part 1, participants can complete the Survivor Self-Assessment online at home or in the waiting room before the clinic appointment.

Similar to Aim 1: Part 1, we will enrich for minorities in the MSK clinic by enrolling no more than 20 white non-Hispanic patients at MSK. After enrolling 20 white non-Hispanic patients from MSK, if we have not yet enrolled 30 total patients from MSK, we will only invite non-white or Hispanic patients to participate until 30 patients enroll. With over 20 new survivors seen in this clinic each month, this will not hinder enrollment.

At each study site, each study participant will receive \$50 from the RSA at their study site to provide thanks for their time and effort immediately following completion of the final study survey. This is less than the \$100 incentive for patients in Aim 1: Part 1 because the time and effort will be less for these participants.

*NP.* We will be asking the MSK and HH NP to provide feedback (via survey and interview) about their experience using HN-STAR. Through the consent process, participants will understand that their NP will be surveyed and interviewed about HN-STAR as part of the study. The NPs responsible for head and neck cancer survivors will be asked to provide written consent to participate.

*Primary care providers.* After a participant has attended the survivorship clinic visit and received the Survivorship Care Plan, their identified PCP will be mailed the Survivorship Care Plan, consistent with current practice. One week later, at each site, the RSA will contact the primary care provider associated with the participant by mail and follow up by telephone to invite them to complete an online survey. Through the consent process, patient participants will understand that their PCPs will be contacted and surveyed as part of the study. The RSA at each site will attempt to recruit all 45 primary care providers by trying to reach them by phone for at least one month but no more than 6 weeks after the initial call. We will not explicitly consent the PCP's, because they will not provide any PHI, and the study is minimal risk. Their participation is optional, and we will consider completion of the survey as agreement to participate. We anticipate that not all 45 PCP's will complete the survey; this is one of the feasibility benchmarks of our study.

PCP's may complete the survey over the phone with the RSA, by paper form and return by mail, or log in to the survey. After completing the online survey, each participating primary care provider will receive a \$100 electronic gift card via email to provide thanks for their time and effort. This anonymous payment procedure has been used successfully in the past as part of protocol (#X09-007, Practice-Based Research Networks (PBRN) Primary Care Providers Survey, PI: [name]).

We anticipate that we will complete recruitment for both Aim 1: Part 1 and Aim 2: Part 2 within 18 months of opening the protocol.

## 7.0 ASSESSMENT/EVALUATION PLAN

Data collection will take place at both MSK and HH by trained RSAs. Patients will be assigned a unique study identification number independent of the patients' medical record number. Data will be stored on the secure MSK network drive housed in the Department of Epidemiology and

Biostatistics at MSK. Interview data will be analyzed jointly with Columbia University, a Data Analysis site.

## 7.1 Usability Assessments

*Aim 1: Part 1: Component pilot testing.* Usability testing will evaluate how easily and appropriately users interact with each component of HN-STAR. We will recruit 10 patients from MSK's Head and Neck Cancer Survivorship Clinic to participate in end-user testing of the self-assessment and the Survivorship Care Plan.

**7.1.1 Survivor Self-Assessment (Appendix A):** Each survivor will arrive 1 hour before their scheduled routine visit at the clinic. He or she will complete the Survivor Self-Assessment with a RSA in a private room in the Survivorship Clinic before a routine visit.

**7.1.2 Survivor Post-Assessment Survey (Appendix D):** Participants will then complete the Survivor Post-Assessment Survey regarding perceptions of information quality, system quality, and usefulness of the Survivor Self-Assessment. Feedback from 10 survivors should identify most usability issues with HN-STAR.

**7.1.3 Survivor Post-Assessment Interview (Appendix N):** After the survivor completes the Survivor Self-Assessment and the Survivor Post-Assessment Survey, the RSA will interview the survivor, asking whether items were clearly presented, whether any symptoms were missed, and whether response options made sense. This conversation will supplement the Survivor Post-Assessment Survey by providing in-depth information when needed. This interview will be audio-recorded.

**7.1.4 Survivorship Care Plan (Appendix C).** After the Post Assessment Interview, the patient will proceed to the clinic visit room for the routine follow-up visit. The NP will use the Interactive Discussion Guide during the clinic visit, and the survivor will receive the automatically generated Survivorship Care Plan at the end of the visit.

**7.1.5 Survivor Post-Visit Survey (Appendix E):** Following the visit, the participant will return to the private room with the RSA to complete the Survivor Post-Visit Survey. The Survivor Post-Visit Survey elicits participant opinion on the role of the Survivor Self-Assessment in the clinic visit and the ease of use of, satisfaction with, and perceived usefulness of the Survivorship Care Plan.

**7.1.6 Survivor Post-Visit Interview (Appendix O):** After the survivor completes the Post-Visit Survey, the RSA will interview the survivor, asking about the ease of use of, satisfaction with, and perceived usefulness of the visit and Survivorship Care Plan. This conversation will supplement the Survivor Post-Visit Survey by providing in-depth information when needed. This interview will be audio-recorded.

**7.1.7 Nurse Practitioner Post-Visit Survey.(Appendix F):** Directly after each clinic visit, the NP will complete one brief online survey for each participant. The Nurse Practitioner Post-Visit Survey focuses on the experience using the Interactive Discussion Guide during the visit. Specifically, it will assess whether the Interactive Discussion Guide presented a complete list of issues for the patient, whether it contained irrelevant information, and the length of the visit. Survey responses will be recorded and stored electronically with Web Core.

**7.1.8 Nurse Practitioner Interview.** After all 10 participants have completed usability testing, the RSA will conduct a qualitative interview with the NP ([name]) to evaluate any problems with, or strengths of, the Interactive Discussion Guide and whether the usefulness or usability of the Interactive Discussion Guide varied by type of patient seen in clinic. This interview will take place with the RSA and the NP in a private office and will be audio recorded. The interview guide is included as Appendix K.

## 7.2 Feasibility Assessments

### *Aim 1: Part 2: Feasibility in clinical practice*

Feasibility testing involves evaluating whether HN-STAR can move forward to evaluation in a clinical trial setting. Before beginning Aim 1: Part 2, we will address findings from Aim 1: Part 1 by making changes to HN-STAR and the accompanying surveys. This will be done once, after the completion of Aim 1: Part 1.

**7.2.1 Survivor Post-Assessment Survey.(Appendix D)** After integrating feedback from Aim 1: Part 1 into HN-STAR and the accompanying surveys, an additional 45 survivors (30 from MSK and 15 from HH) will be recruited and will provide informed consent over the phone (see section 6.0). The participants will complete the Survivor Self-Assessment online (on a computer or tablet, at home or in the clinic waiting room) within two weeks of a routine scheduled visit. The Survivor Post-Assessment Survey (adapted, if needed, from Aim 1: Part 1) will immediately follow the Survivor Self-Assessment. Survey responses will be recorded and stored electronically with Web Core.

**7.2.2 Survivor Post-Visit Survey. (Appendix E)** When the patient comes for the visit, the RSA will be at the clinic and available to answer questions about the study and direct the integration of study flow in clinical practice as needed. Each patient will see the NP (who will use the Interactive Discussion Guide during the visit) and receive the Survivorship Care Plan. The RSA will then bring the patient to the waiting room to complete the Survivor Post-Visit Survey (adapted from Aim 1: Part 1) on a computer or IPad. Survey responses will be recorded and stored electronically with Web Core. The RSA will then provide the patient incentive when the survey is complete.

**7.2.3 Primary Care Provider Survey. (Appendix G)** Two weeks after the visit (when the Survivorship Care Plan is mailed to the PCP), each patients' PCP will be invited to complete a brief online survey regarding whether they received and reviewed the Survivorship Care Plan, as well as the ease of use of, satisfaction with, and perceived usefulness of the Survivorship Care Plan. Survey responses will be recorded and stored electronically by Web Core. The PCP may complete the survey at any time within two months following enrollment.

**7.2.4 Nurse Practitioner Post-Visit Survey.(Appendix F):** Directly after each clinic visit, the NP will complete one brief online survey for each participant. The Nurse Practitioner Post-Visit Survey focuses on the experience using the Interactive Discussion Guide during the visit. Specifically, it will assess whether the Interactive Discussion Guide presented a complete list of issues for the patient, whether it contained irrelevant information, and the length of the visit. Survey responses will be recorded and stored electronically with Web Core.

**7.2.5 Nurse Practitioner Interview:** After all participants in Part 2 have completed usability testing, the RSA will conduct a qualitative interview with the NPs ([name] and [name]) to evaluate any problems with, or strengths of, the Interactive Discussion Guide and whether the usefulness or usability of the Interactive Discussion Guide varied by type of patient seen in clinic. This interview will take place with the RSA and the NP in a private office and will be audio recorded. The interview guide is included as Appendix K.

**7.2.6. Survivor Follow-up Interview:** Six months after the visit, the RSA will conduct a brief interview with the patient to determine adherence to the recommendations in the Survivorship Care Plan. Using the Survivorship Care Plan as a guide, the RSA will ask about whether the patient completed each task that was recommended and whether other providers were involved.

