We developed a web-based, algorithm-driven platform called the **Head and Neck Survivorship Tool: Assessment and Recommendations (HN-STAR)** to address the most salient issues in providing comprehensive survivorship care to head and neck cancer survivors. First, HN-STAR ensures the identification of all late effects by collecting symptom data directly from patients. It then synthesizes patient-reported outcomes, treatment data, and current evidence about survivorship care into a tailored Interactive Discussion Guide. The oncology provider uses the Interactive Discussion Guide in a routine oncology follow-up visit to address all elements of

comprehensive survivorship care. Finally, HN-STAR automatically creates the Survivorship Care Plan based on the clinic visit, which minimizes burden for oncology providers. This Survivorship Care Plan is updated at each visit to incorporate symptom changes, modified management plans, and more current evidence regarding survivorship care.

**The goal of our proposal is to evaluate the feasibility of HN-STAR in the setting of survivorship clinics, in preparation for a future multi-site randomized controlled trial.** The future trial will randomize clinics at multiple centers to use HN-STAR or usual care, and the primary outcomes will be changes in 1) the number of late effects identified and 2) the number of late effects managed in clinic. We will also investigate adherence to recommended care and any changes in health outcomes. The *current protocol* is a necessary feasibility study to inform preliminary outcomes, design, and sample size for the future trial.

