**Figure 4 continued. Outcome collection**

Assessment	Source	Timing (including end of data collection window)
Survivor Post-Visit Survey	Patient	Following clinic visit, before leaving clinic
Primary Care Provider Survey	PCP	At least one week after being mailed Survivorship Care Plan, within a month of enrollment into study
Passively collected feasibility metrics	HN-STAR	Immediate concurrent data collection via Webcore
Nurse Practitioner Interview	NP	After 30 patients have completed Aim 1: Part 2 at MSK and 15 patients have completed Aim 1: Part 2 at HH, within 1 month of last patient completing Aim 1: Part 2 at the respective site
Survivor Follow-up Interview	Patient	Six months after the clinic visit
Preliminary metrics for future trial (Aim 2)		
Oncologic metrics: Late effects identified and addressed, receipt of head and neck surveillance and appropriate follow-up (e.g. dental exam for those who underwent radiation therapy)	Clinic notes, prescriptions or referrals	Abstracted from any time in the year before the visit (pretest) and in the note pertaining to the clinic visit (posttest)
Non-oncologic metrics: Receipt of routine preventive care (e.g., cancer screening, tobacco cessation)	Survivor Self-Assessment	After completion of the Survivor Self-Assessment

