## 11.0 BIOSTATISTICS

**11.1 Sample size.** This feasibility study is not powered to test formal hypotheses. Instead, it will provide feedback regarding the HN-STAR process. We will enroll 10 patients in Aim 1: Part 1. In Aim 1: Part 2, we will enroll 45 additional patients: 30 from MSK and 15 from HH. The MSK clinic sees over 20 patients per month, ensuring that enrollment is attainable. The HH clinic sees approximately 8 patients per month. We anticipate that enrolling 45 patients will not take longer than 6 months. Enrolling PCPs may be more difficult; we anticipate that not all 45 PCPs will complete the Primary Care Provider Survey. Part of our feasibility study is to test whether this method of recruitment and level of incentives will be adequate to recruit PCPs in a future study, and the level of participation will inform this feasibility outcome. Both NPs are integrally involved in implementing HN-STAR in their clinics.

### 11.2 Analysis Aim 1: Parts 1 and 2

The structured survey questions (asked of survivors, NPs, and PCPs in Aim 1: Parts 1 and 2) will be summarized using descriptive statistics. Quantitative outcomes will include survivors' rates of completion of the self-assessment, survey completion rates for survivor, NP, and Primary Care Provider Surveys in the feasibility study. The number of questions to answer is different between surveys and even between respondents, based on skip patterns built into the electronic survey platform. Each survey will be considered complete if at least 75% of questions that are asked are answered. WebCore will automatically capture the percentage of questions that are answered for each survey administered. We will also look at survivor responses by race and ethnicity. Other quantitative outcomes include the median time survivors required to complete the self-assessment, the accuracy of the automated treatment summary (verified against the EMR), the time required for NP verification of the treatment summary, and the length of HN-STAR visits.

Each component of HN-STAR will be evaluated individually for feasibility. We will consider the Survivor Self-Assessment feasible for subsequent effectiveness testing if the following criteria are met:

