**11.3.1 Oncologic outcomes.** We will only investigate late effects that we assess in HN-STAR. (If usability testing identifies additional late effects we did not target in our Survivor Self-Assessment, we will add them to the Survivor Self-Assessment for Aim 1: Part 2 and include them in Appendix H.) For each late effect, we will consider it identified if it was mentioned in a clinic note, and we will consider it addressed if there was a referral,

recommendation, education, or explicit acknowledgement of inaction. (Inaction may be appropriate, because in some cases, when symptoms are persistent and intractable, no intervention may be recommended.) For each patient, we will first count the number of late effects identified. We will then calculate the proportion of identified late effects that are addressed.

We will use descriptive statistics to report each element of oncologic care listed in Appendix H (i.e. smoking cessation, dental exam, blood work for thyroid studies, endoscopic exam, and head and neck physical exam). Each patient may not require every element of follow-up, depending on their primary tumor site or treatment received. We will use the number of recommended elements of care as the denominator, and we will calculate the proportion of these elements that are performed.

**11.3.2 Non-oncologic outcomes.** The non-oncologic outcomes in HN-STAR are collected only once. They include cancer screening, vaccination, and other preventive care elements that are explicitly collected in the Survivor Self-Assessment. Only some of these elements will be recommended for each patient, depending on their age, sex, and behaviors. We will calculate the proportion of recommended elements of non-oncologic care that are performed per patient. In addition, for each element of non-oncologic care, we will calculate the proportion of patients who receive it as recommended.

Findings from Aim 2 will inform whether these metrics can be collected from the EMR and HN-STAR. In addition, they will inform the statistical analysis for the future trial. For oncologic metrics only (Section 9.0, Figure 4), we will calculate the difference before HN-STAR use and after. Differences in oncologic metrics will be used in the power calculation for the proposed randomized trial. Non-oncologic metrics will be reported descriptively to inform the feasibility of collecting these data from self-report.

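### Section 11.3.1 scores surveillance elements as performed, but its posttest stops at the study visit, and the six-month interview that could show later completion has no planned analysis

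*Combined protocol and SAP*

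**What the plan says.** **Collection.** Section 7.2.6 schedules an interview with Part 2 survivors in which "the RSA will conduct a brief interview with the patient to determine adherence to the recommendations in the Survivorship Care Plan". Working from each survivor's care plan, the research assistant will "ask about whether the patient completed each task that was recommended and whether other providers were involved". Figure 4 in Section 9.0 lists the interview under Aim 1: Part 2, timed "Six months after the clinic visit".

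**Posttest.** For oncologic metrics, Figure 4 takes the pretest from the year before the visit and places the posttest "in the note pertaining to the clinic visit (posttest"). Section 7.4.1 and the opening of Section 11.3 set the same end point: surveillance is abstracted for the preceding year and the study visit, and nothing later.

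**Measure.** Section 11.3.1 takes the number of elements recommended for the patient as the denominator, and "we will calculate the proportion of these elements that are performed". It names five elements: smoking cessation, dental exam, thyroid blood work, endoscopic exam, and head and neck physical exam.

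**Use.** Section 11.3.2 sends the before-after differences in oncologic metrics to the power calculation for the randomized trial. Section 3.0 says of that trial: "We will also investigate adherence to recommended care and any changes in health outcomes".

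**The concern.** The measure and its window do not fit together. Section 4.2.4 gives each care plan recommendation a schedule and a responsible party, and Section 4.2.5 allows that party to be the survivor or the primary care provider. By the plan's own account, then, some recommended care may be done after the visit and outside the clinic. A posttest that ends at the visit scores such care as not performed, however promptly it follows.

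Two things are at stake. The before-after difference for surveillance may be too low when it is used to plan the next trial. And adherence, which that trial intends to study, has no defined estimate here, although the plan collects task-by-task data on it.

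**Working it through.** The documents give no figure for adherence or for posttest receipt, so there is none to reproduce. The check traces the sources and then illustrates size under stated assumptions.

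**1. Which sources reach past the visit?**
- Record abstraction of surveillance (Sections 7.4.1 and 11.3): ends at the study visit.
- Non-oncologic care (Sections 7.4.2 and 11.3.2): collected once, before the visit.
- Primary care provider survey (Section 7.2.3): sent after the visit, but it asks about receipt, review and opinion of the care plan, not care completed.
- Survivor follow-up interview (Section 7.2.6): asks about completion of each recommended task at six months.

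Only the last covers completion after the visit.

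**2. Which analysis uses it?**
- Section 11.2 applies interview data to usability in Part 1; this is a Part 2 interview.
- No feasibility criterion in Section 11.2 draws on it.
- Section 11.3 does not mention it.
- The list of stored interview data in Section 13 omits it.

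**3. What counts as receipt?** Section 2.0 (Aim 2) treats referrals, prescriptions and recommendations as indicators of receipt, and Figure 4 gives the oncologic source as clinic notes, prescriptions or referrals. Section 11.3.1 counts elements performed. A referral made at the visit scores under the former reading and not under the latter. The plan does not choose between them.

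**4. Illustration of size, if only performed elements count.** Let m be the number of recommended elements and k the number completed only after the visit. The highest possible posttest proportion is (m − k)/m. Assume a non-smoker who received radiation and for whom the other four elements in Section 11.3.1 are recommended, so m = 4:

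| k (assumed) | Ceiling |
|---|---|
| 0 | 4/4 = 100% |
| 1 | 3/4 = 75% |
| 2 | 2/4 = 50% |
| 3 | 1/4 = 25% |

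The documents do not give k.

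**5. What the interview data could deliver.** Section 11.1 states that "we will enroll 45 additional patients: 30 from MSK and 15 from HH". For a mean of per-patient proportions p among n survivors, an approximate 95% half-width is at most 1.96 × √(p(1 − p)/n), because a quantity between 0 and 1 with mean p has variance no greater than p(1 − p). The adherence levels, and a 20% loss leaving 36 of 45 interviewed, are assumptions.

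| p | n = 45 | n = 36 |
|---|---|---|
| 0.5 | 0.146 | 0.163 |
| 0.7 | 0.134 | 0.150 |
| 0.9 | 0.088 | 0.098 |

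If 36 were reached with a mean of 0.70, counting the other 9 as not completed would give 0.70 × 36/45 = 0.56. Both figures are useful for planning.

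**The case against.** The case on the other side has several parts.

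**Orders may count.** If the Aim 2 wording in Section 2.0 governs, a dental referral or a thyroid order made at the visit is receipt, and the posttest can reach 4/4. This stands as far as it goes. A reader might infer that posttest receipt is understated by construction; the documents do not support that, because they leave open whether orders count. What remains is a conflict with Section 11.3.1 that must be reconciled.

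**The timing is assumed.** Nothing says when dental exams or thyroid blood work take place. Blood could be drawn on the visit day. This also stands, so the 50% ceiling is an example and not an estimate.

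**The visit is the right source for the main metrics.** Late effects identified and addressed are actions at the visit, and Section 3.0 makes identification and management of late effects the future trial's primary outcomes. The point therefore concerns surveillance elements only.

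**The analysis may be implied.** Figure 4 puts the interview under Aim 1: Part 2, so Section 11.2 may be its natural home. Appendix Q, a Part 2 follow-up self-assessment listed but not available here, may be its instrument. If it holds structured questions, the general rule in Section 11.2 to summarize survey questions descriptively might reach it. Even so, that rule sets no denominator and no handling of survivors not reached.

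**Descriptive study.** Section 11.1 says: "This feasibility study is not powered to test formal hypotheses". That removes any concern about testing. It does not cover a difference that the plan carries into a power calculation.

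**Replacing the posttest would do harm.** One might infer that the six-month answers should become the posttest. Subtracting a one-year, record-based pretest from six months of self-report would mix a change in care with changes of source and window. Annual tests, such as the thyroid studies given as an example in Section 4.2.3, may also not fall due within six months. This objection stands, and it shapes the fix.

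**Conclusion.** The point holds for receipt of surveillance and follow-up elements. Under Section 11.3.1 as written, an element completed after the study visit is not counted as performed. Section 2.0 and Figure 4 point to a looser definition, and the resulting difference goes into the future trial's power calculation. The one described source on later completion has no planned analysis.

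The size is unknown. It depends on how many recommended elements are completed after the visit and on whether orders count. The range in the illustration, from no loss to a 25% ceiling, rests entirely on assumed values of k. The documents do not support saying that the posttest cannot capture what HN-STAR recommends, or that the late-effect metrics are affected by this gap.

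**What to change.** Three changes to Section 11:

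- **(a) Define the adherence estimate.** For each Part 2 survivor, report the proportion of Survivorship Care Plan tasks due within six months that the survivor reports as completed at the interview, overall and by Appendix H element. Give a second figure that counts survivors not reached as not completed.
- **(b) Keep it separate.** Present it as a descriptive, self-reported adherence estimate and do not subtract it from the record-based pretest.
- **(c) Restrict the before-after difference.** For the power calculation, limit the visit-based difference to late effects identified and addressed and to elements that can be performed at the visit. Report elements ordered or referred at the visit separately from elements performed, and reconcile Section 2.0 and Figure 4 with Section 11.3.1 on what counts as receipt.

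The cost is mainly analysis wording, since the interview is already scheduled. If the abstraction form in Appendix H, which is not available here, does not already separate ordered from performed, it needs that distinction. The adherence figure will be self-reported, will cover six months only, and will have no matching pretest. The pretest spans a year and the posttest a single visit; these changes do not remove that asymmetry, which should be stated beside the difference.
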